4.4.10.2 Respiratory rate

One minute respiratory rate will be assessed after the patient has been sitting for 5 minutes. Refer to Table 1 through Table 3 for the timing of individual measurements.

4.4.10.3 Oral temperature

Oral temperature will be measured in degrees Celsius (°C).

4.4.11 Height and weight

Height (cm) and weight (kg) will be measured without shoes.

4.4.12 Physical examination

4.4.12.1 Complete physical examination

The complete physical examination will include an assessment of the following: general appearance, skin, head and neck (including eyes, ears and throat), lymph nodes, thyroid, musculoskeletal/extremities (including spine), cardiovascular, lungs, abdomen, and neurological systems.

Complete physical examination data to be recorded on the pCRF will include: 1) normal/abnormal, and 2) a description of any abnormalities. Except for the screening

examination, if there has been no change from the previous exam, only that information need be recorded.

4.4.12.2 Brief Physical Examination

The brief physical examination will include an assessment of the following: general appearance, abdomen, lungs, and the cardiovascular system.

Brief physical examination data to be recorded on the pCRF will include: 1) normal/abnormal, and 2) a description of any abnormalities. If there has been no change from the previous exam, only that information need be recorded.

4.5 Genetic measurements and co-variables

4.5.1 Collection of samples for genetic testing

Patients will provide a blood sample as per the inclusion criteria and visit schedule.

A single venous blood sample (9 mL) will be collected into a polypropylene tube containing ethylenediamine tetra-acetic acid (EDTA) and gently inverted a minimum of five times to mix thoroughly. Tubes will be labeled with the protocol study number, centre number, enrollment code and/or randomization number and date of sample collection. No personal identifiers (patient name, initials or date of birth) will be placed on the tube or accompanying documentation. A record of the date of the patient consent to the genetic research and the date of the blood sample collection will be recorded in the appropriate section of the CRF.

Genotype is a stable parameter; therefore if for any reason the blood sample is not drawn at Visit 2, it may be taken at any visit until the last study visit. The genetic blood sample should ideally be drawn through the same cannula used to draw blood samples required for the main study.

4.5.1.1 Sample processing and shipping

Samples will be frozen (-20°C or below) and transported to the relevant DNA extraction laboratory within one month of collection and must remain frozen at all times. Processing, labelling and shipping instructions are provided in Appendix G.

Genetic blood samples will be sent to the following address:

Where possible samples should be shipped in batches and shipment should be coordinated with the receiving site to ensure that samples arrive within working hours. A requisition sheet, detailing the protocol study number, centre number, enrollment code and/or randomization number and date of sample collection, should accompany the shipment.

4.5.1.2 Storage and coding of DNA samples

The processes adopted for the coding and storage of samples for genetic analysis is important to maintain patient confidentiality.

For all samples irrespective of the type of coding used the DNA will be extracted from the blood sample. The DNA sample will be assigned a unique number replacing the information on the sample tube. Thereafter, the DNA sample will be identifiable by the unique DNA number only. The DNA number will be used to identify the sample and corresponding data at the AstraZeneca genetics laboratories, or at the designated contract laboratory. No personal details identifying the individual will be available to any AstraZeneca employee working with the DNA.

The blood samples and data for genetic analysis in this study will be coded. Each blood sample will be labelled with the study number and patient number. Only the investigator will be able to link the blood sample to the individual patient. The sample and data will not be labelled with a personal identifier. The link between the patient enrollment/randomization code and the DNA number will be maintained. The link will be used to identify the relevant DNA samples for analysis, facilitate the correlations of genotypic results with clinical data, allow regulatory audit and to trace samples for destruction in the case of withdrawal of consent.

All DNA samples will be stored under secure conditions with restricted access at AstraZeneca. The blood, DNA samples or data derived from the samples may be made available to groups or organisations working with AstraZeneca on this study or as part of the development drug project. However, the samples and any results will remain the property of AstraZeneca at all times. AstraZeneca will not give blood, DNA samples or data derived from the samples to any other parties, except as required by law.

Samples will be stored for a maximum of 20 years, from the date of completion of the study, after which they will be destroyed.

DNA is a finite resource that is used up during analysis. Samples will be stored and used until no further analyses are possible. Further samples will not be acquired from patients.

4.5.1.3 Summary of genetic assessments and analysis

The purpose of the genetic component of the study is to generate data for use in future retrospective analyses. Future analyses will explore genetic factors, which may influence the absorption and disposition of, and response to AZD6140 including side effects such as dyspnea. The results of the genetic analyses will not form part of the clinical study report for this study. The results may be pooled with genetic data from other studies on AZD6140 to generate hypotheses to be tested in future studies.

4.6 Volume of blood sampling

The total volume of blood that will be drawn from each patient in this study is as follows:

Assessment		Sample volume (mL)	n of samples	Total volume (mL)
AZD6140 PK samples		2 mL	34	68 mL
Blood Sample for genotyping		9 mL	1	9 mL
β-HCG (females only)		Drawn from chemistry	4	
Safety	Clinical chemistry	10 mL	7	70 mL
	Hematology	5 mL	7	35 mL
Screening	Clinical chemistry	10 mL	1	10 mL
	Hematology	5 mL	1	5 mL
	HIV/HBsAg, hepatitis C	10 mL	1	10 mL
Total				207 ML ^a

Table 6Volume of blood to be drawn from each patient

a. Total blood volume may vary if patient experiences a spontaneous dyspnea episode, which requires a PK (2 ML) sample(s) to be drawn.

4.7 Adverse Events

The methods for collecting adverse events are described below.

4.7.1 Adverse Events

4.7.1.1 Definitions

The definitions of adverse events (AEs), serious adverse events (SAEs) and other significant adverse events (OAEs) are given below. It is of the utmost importance that all staff involved in the study is familiar with the content of this section. The principal investigator is responsible for ensuring this.

Adverse event

An adverse event is the development of an undesirable medical condition or the deterioration of a pre-existing medical condition following or during exposure to a pharmaceutical product, whether or not considered causally related to the product. An undesirable medical condition can be symptoms (eg, nausea, chest pain), signs (eg, tachycardia, enlarged liver) or the abnormal results of an investigation (eg, laboratory findings, electrocardiogram). In clinical studies, an AE can include an undesirable medical condition occurring at any time, including run-in or washout periods, even if no study treatment has been administered.

Serious adverse event

A serious adverse event is an AE occurring during any study phase (ie, run-in, treatment, washout, follow-up), and at any dose of the investigational product, comparator or placebo, that fulfils one or more of the following criteria:

- results in death
- is immediately life-threatening
- requires in-patient hospitalization or prolongation of existing hospitalization
- results in persistent or significant disability or incapacity
- is a congenital abnormality or birth defect
- is an important medical event that may jeopardise the patient or may require medical intervention to prevent one of the outcomes listed above.

The causality of SAEs (ie, their relationship to study treatment) will be assessed by the investigator(s), who in completing the relevant case report form must answer "yes" or "no" to the question "Do you consider that there is a reasonable possibility that the event may have been caused by any of the following – study medication – other medication? "For further guidance on the definition of a SAE and a guide to the interpretation of the causality question, see Appendix B to the Clinical Pharmacology Study Protocol.

Other Significant Adverse Events (OAE)

OAEs will be identified by the Drug Safety Physician and if applicable also by the Study Delivery Team Physician during the evaluation of safety data for the Clinical Study Report. Significant adverse events of particular clinical importance, other than SAEs and those AEs leading to discontinuation of the patient from study treatment, will be classified as OAEs. Examples of these are marked haematological and other laboratory abnormalities, and certain events that lead to intervention (other than those already classified as serious), dose reduction or significant additional treatment. For each OAE, a narrative may be written and included in the Clinical Study Report.

4.7.1.2 Recording of adverse events

The patients will be told to report any AE occurring during the study to the investigator or his personnel. Open standardized AE questioning, such as "Have you had any health problems since the previous visit?" will be done by the investigators or their personnel at each contact with the patient. The AE open standardized questioning should be done discretely in order to prevent the patients from influencing each other.

Any AEs observed or reported by a patient and/or staff, will be recorded in the CRF. Any AE including clinical findings not resolved at the follow-up visit, will be followed up at an additional visit or telephone contact within 7 days after the follow-up visit or until resolved or explained.

Laboratory and vital sign abnormalities will not be recorded as an AE unless any criterion for an SAE is fulfilled, the patient discontinues the study due to the result(s), or the investigator insists that it should be reported as an AE. If a laboratory value or vital sign is associated with clinical signs and symptoms, the signs and symptoms should be reported as an AE and the associated laboratory or vital signs should be considered additional information. Any sign or symptom that fulfills the SAE definition (Appendix B) or is the reason for discontinuation of treatment of investigational products should be reported accordingly.

The following variables will be recorded for each AE noted:

- Onset, resolution
- Intensity (mild/ moderate/ severe)
- Action(s) taken
- Outcome of the AE
- Causality of the AE (yes or no)
- Whether it constitutes an SAE or not

The intensity rating is defined as:

- 1 = mild (awareness of sign or symptom, but easily tolerated)
- 2 = moderate (discomfort sufficient to cause interference with normal activities)
- 3 = severe (incapacitating, with inability to perform normal activities)

It is important to distinguish between serious and severe AEs. Severity is a measure of intensity whereas seriousness is defined by the criteria in Section 4.7.1.1. An AE of severe intensity need not necessarily be considered serious. For example, nausea that persists for several hours may be considered severe nausea, but not a SAE. On the other hand, a stroke that results in only a limited degree of disability may be considered a mild stroke but would be a SAE.

4.7.1.3 Reporting of serious adverse events

Investigators and other site personnel must inform appropriate AstraZeneca representatives of any SAE that occurs in the course of the study within 1 day (ie, immediately but no later than the end of the next business day) of when he or she becomes aware of it.

The AstraZeneca representative will work with the investigator to compile all the necessary information and ensure that the appropriate AstraZeneca Drug Safety Department receives a report by day one for all fatal and life-threatening cases and by day five for all other SAEs.

Follow-up information on SAEs must also be reported by the investigator within the same time frames.

If a non-serious AE becomes serious, this and other relevant follow-up information must also be provided to AstraZeneca within 1 day as described above. For a non-serious AE that become serious but which is not fatal or life-threatening a report should be received within 5 days.

All SAEs have to be reported, whether or not considered causally related to the investigational product or to the study procedure(s). All SAEs will be recorded in the case report form. The investigator is responsible for informing the Ethics Committee and/or the Regulatory Authority of the SAE as per local requirements.

5. STUDY MANAGEMENT

5.1 Monitoring

5.1.1 Study monitoring

The monitoring of this study will be performed in accordance with the principles of Good Clinical Practice (GCP) as laid out in the International Conference on Harmonization (ICH) document "Good Clinical Practice: Consolidated Guideline".

The specific requirements of the genetic part of the study will be discussed with the investigator(s) (and other personnel involved with the study.

5.1.2 Data verification

It is a prerequisite of this study that the study monitor has direct access to source data for data verification. This will be done by comparing data from the pCRFs with those in the patient's medical notes (permission from the patient will be sought as part of the consent process). Such verification is an essential element of quality control, as it allows the rectification of transcription errors and omissions.

Monitoring including source data verification should routinely be performed prior to the transfer of data to Data Management.

Source verification of the genetic consent of participating patients will be performed and make sure that the investigational team is adhering to the specific requirements of the genetics aspects of the study.

5.1.3 Archiving of study documentation

AstraZeneca will retain all documentation pertaining to this study in AstraZenca for central file for as long as AZD6140 is available for human consumption.

The investigator will retain all documentation pertaining to this study for at least 15 years.

Amended Clinical Pharmacology Protocol Study Code D5130C00034 Edition Number 4.0 Date

5.2 Audits and inspections

Authorized representatives of AstraZeneca, a regulatory authority, an Independent Ethics Committee (IEC) or an Institutional Review Board (IRB) may visit the centre to perform audits or inspections, including source data verification. The purpose of an AstraZeneca audit or inspection is to systematically and independently examine all study related activities and documents to determine whether these activities were conducted, and data were recorded, analysed, and accurately reported according to the protocol, GCP guidelines of the ICH and any applicable regulatory requirements. The investigator should contact AstraZeneca immediately if contacted by a regulatory agency about an inspection at his or her centre.

5.3 Training of staff

The principal investigator will maintain a record of all individuals involved in the study (medical, nursing and other staff). He or she will ensure that appropriate training relevant to the study is given to all of these staff, and that any new information of relevance to the performance of this study is forwarded to the staff involved.

Before the first patient is entered into the study the investigational staff will have an opportunity to discuss the procedures associated with the collection of blood samples, extraction of DNA and genetic testing with AstraZeneca personnel. The ethical considerations specific to genotyping and the importance of the informed consent process will be made clear. The requirements for the collections of the patients' sample will also be made clear.

5.4 Changes to the protocol

Study procedures will not be changed without the mutual agreement of the principal investigator and AstraZeneca.

If it is necessary for the study protocol to be amended, the amendment and/or a new version of the study protocol must be notified to or approved by each IEC or IRB, and in many countries also the local regulatory authority, before implementation. Local requirements must be followed.

If a protocol amendment requires a change to a particular center's Master Informed Consent Form, then AstraZeneca and the centre's IEC or IRB must be notified. Approval of the revised Master Informed Consent Form by AstraZeneca and by the IEC or IRB is required before the revised form is used.

AstraZeneca will distribute amendments and new versions of the protocol to each principal investigator(s) who in turn is responsible for the distribution of these documents to his or her IEC or IRB, and to the staff at his or her centre. The distribution of these documents to the regulatory authority will be handled according to local practice.

5.5 Study agreements

The principal investigator at each centre must comply with all the terms, conditions, and obligations of the study agreement for this study. In the event of any inconsistency between this protocol and the study agreement, this protocol shall prevail.

Specific reference to genetics should be included in the agreement. The contractual obligations should not include any additional payment for collecting the samples, unless special processing is required.

5.6 Study timetable and end of study

The study is expected to start in April 2005 and to be completed by May 2006.

5.7 Data management

5.7.1 Case report forms

Paper CRFs (pCRFs) will be used to record all data not captured electronically. Data should be recorded legibly onto the pCRFs in blue or black ballpoint pen. Correction fluid or covering labels must not be used

The AstraZeneca Monitor will check data at the monitoring visits to the investigational site. The Investigator will ensure that the data in the pCRFs are accurate, complete and legible.

Data from the completed pCRFs will be entered onto AstraZeneca's clinical study database and validated under the direction of the Data Manager. Any missing, impossible or inconsistent recordings in the pCRFs will be referred back to the Investigator using a data query form (DQF), and be documented for each individual patient before clean file status is declared.

5.7.2 Pharmacogenetic data

In the case of genotypic data, only the date the patient gave consent to participation in the genetic component of the study and the date the blood sample was taken from the patient will be recorded in the pCRF and database.

The genotypic data generated from the study will be stored in the AstraZeneca LIMS database or other appropriate system. This database is a secure database, which is separate to the clinical database. Some or all of the clinical study dataset may be duplicated within the AstraZeneca LIMS database for exploratory genetic analysis.

However, some or all of the clinical study dataset may be duplicated within the AstraZeneca LIMS database or other appropriate system for exploratory analysis.

5.8 Reporting of Genotypic Results

Results from any genetic research performed will be reported separately from the clinical trial report. AstraZeneca will not provide individual genotype results to patients, their family members, any insurance company, an employer, clinical study investigator, general physician or any other third party, unless required to do so by law. The patient's DNA will not be used for any purpose other than those described in the study protocol.

Individual patients will not be identified in any report or publication resulting from this work. The data and results of this study may be reviewed with collaborators and published, but neither the patient's name nor any other personal identifiers will appear in any publication or report.

6. PHARMACOKINETIC, PHARMACODYNAMIC, SAFETY, GENETIC AND STATISTICAL METHODOLOGY

6.1 Pharmacokinetic / pharmacodynamic evaluation

6.1.1 Calculation or derivation of pharmacokinetic variables

The pharmacokinetic analyses will be performed by Clinical Pharmacokinetics, Experimental Medicine, AstraZeneca , Wilmington, DE.

Plasma concentrations of AZD6140 and its metabolite AR-C124910XX will be listed and depicted graphically as a function of time relative to Day 1 dose for the 2 cohorts. Pharmacokinetic parameters listed below will be estimated by non-compartmental analysis.

Day 1: C_{max} , t_{max} , AUC₀₋₁₂ of AZD6140 and AR-C124910XX, and metabolite to parent C_{max} and AUC ratios

Day 4: C_{max} , t_{max} , AUC_{τ}, metabolite to parent C_{max} and AUC ratios of AZD6140 and AR-C124910XX and, AZD6140 steady state CL/F.

AZD6140 and AR-C124910XX C_{max} will be estimated as the highest measured concentration and t_{max} will be the time to maximum concentration within a dosing interval on Days 1 and 4. AUC₀₋₁₂ and AUC_{τ} will be calculated using the linear trapezoidal method over the 12 hour dosing interval on Days 1 and 4, respectively. AZD6140 CL/F will be estimated as the ratio of AZD6140 dose and AUC_{τ} on Day 4. The ratio of AR-124910XX C_{max} to AZD6140 C_{max} ratio and, AR-124910XX AUC to AZD 6140 AUC ratio will be calculated on Days 1 and 4.

6.1.2 Calculation or derivation of pharmacodynamic variables

Changes from baseline in each period for respiratory parameters will be calculated.

6.1.3 Calculation or derivation of pharmacokinetics/pharmacodynamics

Relationship between AZD6140 concentration and PD endpoints will be explored graphically.

6.2 Safety evaluation

6.2.1 Calculation or derivation of safety variables

Changes from baseline for the safety data (adverse events, vital signs, 12-lead ECG, physical examination data, laboratory data) will be calculated.

6.3 Genetics as a co-variate (not applicable)

6.4 Statistical methods and determination of sample size

6.4.1 Statistical evaluation

A comprehensive Statistical Analysis Plan (SAP) will be prepared and finalized before database lock. The goal of this analysis is to assess the effect of AZD6140 on the respiratory parameters in mild asthma and mild to moderate COPD elderly patients.

6.4.2 Description of analysis sets

6.4.2.1 Pharmacodynamic analysis set

All patients who have evaluable respiratory measurements in both periods of the study without any protocol deviations deemed to affect the pharmacodynamics of AZD6140 will be included in the summaries and listings of the pharmacodynamic data.

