The respiratory parameters, and changes from baseline, will be summarized at each scheduled time point by treatment and visit using descriptive statistics. These will also be supported with graphical displays in order to ease making comparisons.

The plasma concentrations and pharmacokinetic parameters of AZD6140 and AR-C124910XX will be descriptively summarized. Furthermore, graphical plots of the respiratory parameter and concentration of AZD6140 will also be explored.

Safety data (adverse events, vital signs, 12-lead ECGs, laboratory data, physical examination data) will be summarized at each scheduled time point by treatment for each of the 2 cohorts using descriptive statistics.

The results of genetic analysis will be exploratory and will not be included in the clinical study report.

TABLE	OF CONTENTS	PAGE
	TITLE PAGE	1
	PROTOCOL SYNOPSIS	3
	TABLE OF CONTENTS	7
	LIST OF ABBREVIATIONS AND DEFINITION OF TERMS	12
1.	INTRODUCTION	15
1.1	Background	15
1.2	Rationale	16
2.	STUDY OBJECTIVES	17
2.1	Primary objective	17
2.2	Secondary objective(s)	17
3.	STUDY PLAN AND PROCEDURES	17
3.1	Overall study design	17
3.1.1	Screening/Visit 1	
3.1.2	Period I/Visit 2	18
3.1.3 3.1.4	Period II/Visit 3	19
3.1.5	Follow-up/Visit 4	20
3.2	Rationale for study design, doses and control groups	25
3.3	Selection of study population	27
3.3.1	Study selection record	27
3.3.2	Inclusion criteria	27
3.3.3	Exclusion criteria	27
3.3.4	Restrictions	
3351	Criteria for discontinuation	
3.3.5.2	Procedures for discontinuation	
3.3.5.3	Procedures for Discontinuation from Genetic aspects of the study	31
3.4	Treatment(s)	32
3.4.1	Investigational Product(s)	32
3.4.1.1	Identity of investigational product	32
3.4.1.2	Labelling	33
3.4.1.3	Storage	
5.4.1.4 2.4.2	Accountability	
3.4.2 3.1.2	Method of assigning patients to treatment groups	
344	Blinding and procedures for unblinding the study	
5.1.1	2 mang and procedures for anomanig the study	

3.4.4.1	Methods for ensuring blinding	
3.4.4.2	Methods for unblinding study	
3.4.5	Concomitant medication	
3.4.6	I reatment compliance	
4.	MEASUREMENT OF STUDY VARIABLES	37
4.1	Medical examination and demographic measurements	37
4.1.1	Enrollment medical examination and demographic measurements	
4.1.2	Post-study medical examination	38
42	Pharmacokinetic measurements	38
421	AZD6140 and AR-C124910XX	38
4211	Determination of drug concentration in biological samples	38
4.2.1.2	Collection and processing of biological samples for determination of	

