2. STUDY OBJECTIVES

2.1 **Primary objective**

The primary objective of the study is to:

• Assess the effect of AZD6140 on respiratory rate and minute ventilation.

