If a dyspnea episode manifests intermittent symptoms within short time intervals (hours), generally if symptoms are similar and no initial abnormalities are observed on assessments, repeat assessments may be performed as needed at the investigator's judgement to monitor the patient's condition. Other diagnostic studies, such as arterial blood gas (ABG), echocardiogram, or chest x-ray, may be performed to evaluate dyspnea at the investigator's discretion.

If a dyspnea episode subjectively worsens, assessments should be repeated at the investigator's discretion. The patient's dyspnea should resolve, or return to patient's baseline respiratory parameters, before patient proceeds on to Period II (see Section 3.3.5.1).

Patients will be discharged from the study center on Study Day 5, after the completion of all protocol-driven procedures and assessments and at the discretion of the investigator. At discharge, patients will be reminded of the study restrictions listed in Section 3.3.4 and instructed when to return for admission to Period II.

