3.3.5 Discontinuation of patients from treatment or assessment

3.3.5.1 Criteria for discontinuation

Patients may be discontinued from study treatment and assessments at any time. Specific reasons for discontinuing a patient from this study are:

- Voluntary discontinuation by the patient, who are at any time free to discontinue their participation in the study without prejudice to further treatment
- Safety reasons as judged by the investigator and/or AstraZeneca including moderate to severe dyspnea that does not resolve or return to patient's baseline within 2 weeks.
- Severe non-compliance to protocol as judged by the investigator and/or AstraZeneca.

- Incorrect enrollment (ie, the patient does not meet the required inclusion/exclusion criteria) or randomization (ie, the patient is not allocated study drug as described in the protocol) of the patient.
- Patient lost to follow-up
- A suspected/manifested infection according to WHO risk categories 2, 3, and 4 (Refer to Appendix D).
- Non-exercising respiratory rate >25 per minute, heart rate >120 per minute or SaO_2 <85%; or FEV1 < 1 Liter; or Peak Expiratory flow < 80L/min; or negative change in Modified Borg Scale /Bidirectional Dyspnea scale >3 points on 2 successive assessments (exclude exercising). All these criteria should be at investigator's judgment in conjunction with clinical findings.

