3.4.3 Method of assigning patients to treatment groups

Written informed consent will be obtained before enrollment and the volunteers identified with an enrollment number starting with E0001001. Patients fulfilling the eligibility criteria will be assigned patient numbers starting with either number **201** (Cohort A) or **301** (Cohort B).

Using the AZ Global Randomization system (Grand) by AstraZeneca LP, patients treatment will be allocated as generated by the system.

Cohort	Volunteer Type	Randomization Number
А	Mild Asthma	201, 202, 203, 204, etc.
В	Mild to moderate COPD	301, 302, 303, 304, etc.

Patients will be randomized strictly sequentially within their Cohort as patients are eligible for randomization on Day 1 of Period I before study drug administration. Written informed consent

will be obtained before enrollment and the volunteers identified with an enrollment number starting with E0001001. Using the AZ Global Randomization system (Grand) by AstraZeneca LP, patient treatment will be allocated as generated by the system. Patients fulfilling the eligibility criteria will be assigned patient numbers starting with number 201, 202, 203, 204, etc.

Patients will be randomized strictly sequentially as patients are eligible for randomization on Day 1 of Period I before study drug administration. If a patient should be incorrectly randomized, randomization should continue with no attempt to correct the error. If a patient discontinues from the study, the randomization number will not be re-used and the patient will not be allowed to reenter the study. Patients who withdraw after having received study medication will not be replaced.

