4.4.2 Inclusion and exclusion criteria

The inclusion and exclusion criteria must be assessed and reviewed with each patient at the screening visit, Day -1 of Periods I and II in order to establish and confirm their eligibility to participate in the study.

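### The both-periods rule for the pharmacodynamic set can drop patients stopped on AZD6140 in Period I for the respiratory effect under study, biasing the estimate towards zero by an unknown amount

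*Combined protocol and SAP*

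**What the plan says.** The primary objective (section 2.1) is to "Assess the effect of AZD6140 on respiratory rate and minute ventilation". Each patient receives AZD6140 and placebo in sequence AB or BA (section 3.4.2).

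- **Analysis set.** Section 6.4.2.1 limits the pharmacodynamic summaries and listings to "All patients who have evaluable respiratory measurements in both periods of the study without any protocol deviations deemed to affect the pharmacodynamics of AZD6140".
- **Stopping.** Section 3.3.5.1 provides for discontinuation from both treatment and assessments. Its list includes "Non-exercising respiratory rate >25 per minute, heart rate >120 per minute", low SaO2, FEV1 or PEF, a change in the dyspnea scales, and moderate to severe dyspnea unresolved within two weeks. The numerical criteria are left to the investigator's judgment.
- **Entry to Period II.** Section 3.1.2: "The patient's dyspnea should resolve, or return to patient's baseline respiratory parameters, before patient proceeds on to Period II". Section 4.4.2 has the entry criteria reviewed at screening and on "Day -1 of Periods I and II in order to establish and confirm their eligibility to participate in the study".
- **No replacement or return.** Section 3.4.3: "Patients who withdraw after having received study medication will not be replaced". A patient who discontinues may not re-enter.
- **Analysis.** Section 6.4.3 plans no formal statistical analysis. The synopsis says that respiratory parameters "will be summarized at each scheduled time point by treatment and visit using descriptive statistics".

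**The concern.** The study was set up to look for a respiratory effect, at a loading dose chosen to give the best chance of provoking dyspnea (section 3.2). Some of the grounds for stopping are the outcome itself or close relatives of it. Under the both-periods rule, a patient stopped on drug in Period I contributes nothing to the main displays, not even the readings that led to the stop. If such patients exist, the respiratory summary is drawn from those who tolerated the drug better. Because no test or model is planned, these means, plots and listings are the whole primary result.

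One related inconsistency affects who is stopped. Section 3.3.5.1 refers to a negative change of more than 3 points on the dyspnea scales, whereas Appendix F scores negative values as improvement, and lower Borg scores mean less breathlessness. These passages must be reconciled.

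**Working it through.** The plan has no figure to reproduce: section 6.4.4 bases the sample size on feasibility and states no dropout rate. Randomizing 12 per cohort for 8 completers implies a tolerated loss of 1 − 8/12 = 33%.

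**Step 1: who leaves the set.**

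| Patient | Period I data | Period II data | In the pharmacodynamic set? |
|---|---|---|---|
| AB, stopped for good on AZD6140 in Period I | up to the stop | none | No |
| BA, stopped on AZD6140 in Period II | complete, on placebo | up to the stop | Can be, if evaluable |
| BA, stopped for good on placebo in Period I | up to the stop | none | No (pushes the other way) |

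The pharmacokinetic set (6.4.2.2) and the safety set (6.4.2.3) have no both-periods rule. No section gives an all-dosed pharmacodynamic display or a missing-data rule.

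**Step 2: size of the bias.** Let a share r of patients react with mean effect D and the rest not at all, so that the true mean effect is rD. Let a share s of reactors be stopped while on drug. With 1:1 sequences (assumed; the ratio is not stated), half of those stops fall in Period I. The set then holds reactors r(1 − s/2) among patients 1 − rs/2, so

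retained / true = (1 − s/2) / (1 − rs/2).

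Section 3.2 reports dyspnea in about 20% of patients at 400 mg in DISPERSE, used here as r. The values of s are assumptions, and r = 10% and 30% are shown for range.

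| s | r = 10% | r = 20% | r = 30% |
|---|---|---|---|
| 10% | 95.5% | 0.95/0.99 = 96.0% | 96.4% |
| 25% | 88.6% | 0.875/0.975 = 89.7% | 90.9% |
| 50% | 76.9% | 0.75/0.95 = 78.9% | 81.1% |
| 100% | 52.6% | 0.50/0.90 = 55.6% | 58.8% |

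**Step 3: chance that it happens at all.** If each AB patient is stopped on drug in Period I with probability q, the chance of at least one loss among n AB patients is 1 − (1 − q)^n, with n = 6 per cohort and 12 over both. Section 3.2 mentions one dyspnea discontinuation, with 163 exposed to AZD6140 across four regimens. The other values of q are assumptions.

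| q | One cohort (n = 6) | Both cohorts (n = 12) |
|---|---|---|
| 1/163 | 3.6% | 7.1% |
| 5% | 26% | 46% |
| 10% | 47% | 72% |
| 20% | 74% | 93% |

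The two steps connect through q = rs: at r = 20%, q = 10% corresponds to s = 50%.

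**Step 4: simulation on respiratory rate.** Cohorts of 12 (6 per sequence) were simulated, removing anyone with two successive Period I resting rates above 25 on either treatment. Assumptions: resting mean 16 to 20 per minute, between-patient SD 3, within-patient SD 2.

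| True effect (breaths/min) | SD of drug effect | Both-periods set | All dosed patients |
|---|---|---|---|
| 0 | 0 | 0.00 | 0.00 |
| +2 | 0 to 4 | 1.46 to 2.00 | 2.00 |
| +4 | 2 to 4 | 3.27 to 3.91 | 3.99 to 4.01 |

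The loss grows with the variation in drug effect between patients and with the resting rate. The all-dosed result assumes that readings up to the stop represent the active period.

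**The case against.** The strongest reply is that few patients may be lost. Section 3.2 says that most dyspnea in DISPERSE was mild and settled while dosing continued, and that no bronchospasm was found in those evaluated. The stopping criteria need the investigator's judgment. Section 3.1.3 sets a minimum washout and no maximum, so a patient with a passing reaction can still enter Period II. This stands, and the bias may be near zero. It does not settle the matter, because these patients have lung disease and receive a dose meant to provoke the symptom.

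Second, the safety set keeps every dosed patient. Dyspnea adverse events remain visible by treatment, and respiratory rate is also listed as a vital sign (4.4.10.2, summarized under 6.4.3.4). This too stands. Minute ventilation, the other primary variable, is not among the listed safety data, nor are spirometry or the dyspnea scales.

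Third, the study is exploratory, paired data are a familiar choice in a two-period crossover, evaluability is decided before unblinding (3.4.4.2), and section 6.4.1 leaves a comprehensive SAP to follow. Blinding does not help, because absence of Period II data excludes the patient mechanically. A paired display can still be kept alongside. The later SAP is the natural place for the change.

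A reader might also infer that the plan leaves out the Table 3 measurements taken during dyspnea, since the synopsis speaks of scheduled time points. The documents do not establish this. Section 6.4.3.1 refers to each time point without that limit, and section 6.4.3.3 plans individual plots against concentration. The coverage is unclear rather than excluded.

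**Conclusion.** The rule makes exclusion from the main pharmacodynamic displays depend on response and sequence. If AZD6140 raises respiratory rate, as section 3.2 hypothesizes, the net bias is towards zero; with no drug effect, the simulation shows none. At 20% reactors the retained share of the effect runs from about 96% to 56%, depending on how many reactors are stopped. The chance of any such loss over both cohorts is about 7% at the DISPERSE discontinuation count and 72% at an assumed 10% stop rate. All of this rests on assumed 1:1 sequences and assumed stopping rates.

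Two stronger readings are tempting. One is that 44% of the effect would be lost, taking the 20% dyspnea rate as the stopping rate. That figure counts reports of dyspnea, and the loss follows only if every reactor is stopped. The other is that all reactors leave the set and the estimate falls to zero. Section 6.4.2.1 asks for evaluable measurements in both periods, not completed periods, so BA reactors can remain. Nor is false reassurance certain, given the safety set.

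Severity: should-fix.

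**What to change.** In section 6.4.2.1 and the SAP, before database lock:

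- Define the main pharmacodynamic set as all dosed patients with a pre-dose and at least one post-dose respiratory measurement in any period. Summarize descriptively by treatment received, using all values up to withdrawal.
- Keep the both-periods set as a sensitivity display.
- List patients stopped early by treatment, with their last values.
- State that Table 3 episode values are listed and summarized by treatment.

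A mixed model that accepts one-period patients is optional, since no formal analysis is planned. The cost is wording only; the data are already to be collected. The downside is that one-period patients add some between-patient noise to the treatment comparison.
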